## **19. APPENDICES**

**Appendix 1 Study Flow Chart of Assessments**

**Appendix 2 WHO Performance Status**

**Appendix 3 Study Acknowledgement / Protocol Signature Page**

**Appendix 4 Summary of Protocol Amendments**

---

CONFIDENTIAL

Immodulon Therapeutics Ltd.  
[name]

## Appendix 1

### Study Flow Chart of Assessments

	Screening Phase	Treatment Phase								
		Day / Week		Day -28 to 0		Week 				
		Day 0	4, 8, 12, 16, 20	24	28, 32, 36, 40, 44	48	52, 56, 60, 64, 68	72	76, 80, 84, 88, 92	96 
Visit window (± days) 	-	-	14	14	14	14	14	14	14	14
Informed Consent	✓									
Inclusion/Exclusion Criteria	✓									
Demography & Baseline Data	✓									
Complete Medical History	✓									
Disease Staging	✓									
Blood Samples for Exploratory Endpoints 		✓		✓		✓		✓		✓
Urine Pregnancy Test 	✓									
IMM-101 Administration		✓	✓	✓	✓	✓	✓	✓	✓	✓
Check time interval since last dose of IMM-101 is ≥14 days		✓	✓	✓	✓	✓	✓	✓	✓	✓
Assess Injection Site Reactions 	✓ 	✓ 	✓	✓	✓	✓	✓	✓	✓	✓
Prior/Concomitant Therapy 	✓	✓	✓	✓	✓	✓	✓	✓	✓	✓
Adverse Event Reporting 	✓	✓	✓	✓	✓	✓	✓	✓	✓	✓

1. The dose given and/or the interval may be modified at the discretion of the Investigator provided the minimum period between doses is no less than 14 days.
2. Inclusion/exclusion criteria will be re-checked before commencing any study treatment.
3. Should the study continue beyond 96 weeks, the same pattern of assessments will continue for subsequent visits as described in this flow chart.
4. Urine pregnancy tests should be repeated as warranted during the study.
5. Nominal week numbers are stated.
6. Check for pre-existing injection site reactions.
7. If the dosing interval is increased, the patient should still attend the study site for safety assessments preferably every 3 months but, if this is not possible, every 6 months at a minimum. The blood sample for exploratory analysis should continue to be taken every 6 months. In addition, if the patient does not attend the clinic for a study visit within a calendar month, the clinic will telephone the patient to enquire about injection site reactions, adverse events, concomitant medications and any other concerns.

## **Appendix 2**

### **WHO PERFORMANCE STATUS**

WHO performance status assessment:

Grade	
0	Asymptomatic (Fully active, able to carry on all pre-disease activities without restriction)
1	Symptomatic but completely ambulatory (Restricted in physically strenuous activity but ambulatory and able to carry out work of a light or sedentary nature. For example, light housework, office work)
2	Symptomatic, <50% in bed during the day (Ambulatory and capable of all self care but unable to carry out any work activities. Up and about more than 50% of waking hours)
3	Symptomatic, >50% in bed, but not bedbound (Capable of only limited self-care, confined to bed or chair 50% or more of waking hours)
4	Bedbound (Completely disabled. Cannot carry on any self-care. Totally confined to bed or chair)
5	Death

Oken *et al* (1982) [6]

---

CONFIDENTIAL

Immudalon Therapeutics Ltd.  
[name]

### Appendix 3

### **SUMMARY OF PROTOCOL AMENDMENTS**

#### **PROTOCOL AMENDMENT 1.0**

This Protocol amendment, dated 21st November 2011, addressed the following change to the study Protocol (Final Version 1.0, dated 15th September 2011):

1. To reduce the volume of blood taken at six monthly intervals for the analysis of exploratory immunological endpoints.

This Protocol Amendment was considered **non-substantial**.

#### **PROTOCOL AMENDMENT 2.0**

This Protocol amendment, dated 13 February 2012, addressed the following changes to the study Protocol (Final Version 2.0, dated 21st November 2011):

1. A change in the third party contract responsible for SUSAR reporting. The responsibility for SUSAR reporting was transferred from Theradex (Europe) Limited to Emas Ltd., Hitchin, Herts., UK

This Protocol Amendment was considered **non-substantial**.

#### **PROTOCOL AMENDMENT 3.0**

This Protocol amendment, dated 25th June 2012 addressed the following changes to the study Protocol (Final Version 3.0, dated 13th February 2012):

- Change in the identity and site of the drug substance manufacturer.
- Change in Vial Size
- Revised Fax Number for the Pharmacovigilance Service Provider

This Protocol Amendment was considered **non-substantial**.

#### **PROTOCOL AMENDMENT 4.0**

This protocol amendment, dated 1st November 2013 addressed the following changes to the study Protocol (Final Version 4.0, dated 1st July 2012):

- Inclusion of collection of information on subject status following withdrawal from the study subject to provision of informed consent

This Protocol Amendment was considered **non-substantial**.

#### **PROTOCOL AMENDMENT 5.0**

This protocol amendment, dated 28th July 2014 addressed the following changes to the study Protocol (Final Version 5.0, dated 1st November 2013):

---

CONFIDENTIAL

Immudulon Therapeutics Ltd.  
[name]

- Clarification of need for study safety assessments (assessment of injection site reactions, recording of adverse events and concomitant medications) to be taken preferably every 3 months but, if not possible due to patient availability, every 6 months at a minimum.
- Clarification of reason for decreasing dose of study medication or increasing dosing interval due to previous injection site reactions.
- Change of Medical Director from [name] to [name]

This Protocol Amendment was considered **non-substantial**.

#### **PROTOCOL AMENDMENT 6.0**

This protocol amendment, dated 7 November 2014 addressed the following changes to the study Protocol (Final Version 6.0, dated 28th July 2014):

- Inclusion of the requirement that, if the patient does not attend the clinic for a study visit within a calendar month, the clinic will telephone the patient to enquire about injection site reactions, adverse events, concomitant medications and any other concerns the patient may have. Details of the call will be recorded in the patient notes with appropriate information on adverse events and concomitant medications also being recorded in the CRF. The maximum volume of blood collected per patient at a single visit (at approximately six-monthly intervals) specifically for the exploratory endpoints has been changed from 'will not exceed 5.0 mL' to 'will not exceed 6.0 mL' as the correct vacutainer is available in a 6 mL size.

This Protocol Amendment was considered **non-substantial**.

#### **PROTOCOL AMENDMENT 7.0**

This protocol amendment, dated 05 June 2015 addressed the following changes to the study Protocol (Final Version 7.0, dated 7 November 2014):

- To show the inclusion of St George's Hospital as an additional site.
- To show the change of address of Immodulon Therapeutics.
- Update the IMP out of fridge storage recommendation from 'The product must be used within 2 hours of being removed from the fridge' to 'The product must be used with 6 hours from being removed from the fridge'.
- Addition of the out of hours telephone number.
- To remove progression-free survival from the study endpoints, due to no protocol-specified assessment schedule for CT scans.
- To amend the presentation of the reduction in metastatic disease data to data listings only, due to CT scans not being a protocol-specified requirement, and change is recorded relative to previous assessment.

---

CONFIDENTIAL

Immodulon Therapeutics Ltd.  
[name]

1. INTRODUCTION

The study explores the long-term safety and tolerability of continued administration of IMM-101 in patients who were previously enrolled in the Phase I safety and tolerability study, IMM-101-001. IMM-101-001 was a first-in-human (FIH), open-label, dose-escalation, intra-patient, placebo-controlled study, in adult patients with confirmed diagnosis of stage III or IV melanoma to evaluate the safety and tolerability of three doses of IMM-101 (further details are available in the FIH study clinical study report [CSR]).

In this long-term follow-up (LTF) study, IMM-101-008, IMM-101 (10 mg/mL) is administered as a single 0.1 mL intradermal injection every 4 weeks or as close to this interval as permitted due to practical or logistical considerations until death or withdrawal, unless such therapy is contraindicated, the patient does not wish to continue, or the study is terminated by the Sponsor.

The duration of this study is determined by the time to death or withdrawal of the last patient remaining in this study, hence the total duration of the study is not pre-determined.

This Statistical Analysis Plan (SAP) describes the intended statistical evaluation of the study data at the time of final study reporting based on the final study database.

This SAP is based on the study protocol (version 9.0, dated 18 October 2017, incorporating amendment numbers 1.0 to 8.0) and the final study case report form (CRF), version 4, dated 02 December 2012, the amended adverse event (AE) CRF version 3, dated 15 October 2013, and Post-Study Long Term Survival Status CRF version 1.0, dated 28 September 2015.

This SAP incorporates the original objectives outlined in the study protocol, the approved SAP dated 08 October 2015 and further amendments combining relevant data from the FIH study IMM-101-001 with the final study data for the LTF study IMM-101-008, in IMM-101-008-enrolled patients, thus providing an evaluation of the long-term safety profile of IMM-101 from first dosing in the FIH study through to last dosing in the LTF study, including the period between studies when patients were treated with IMM-101 under the Immodulon Named Patient Programme (NPP), when relevant data has been recorded in the LTF study CRF.

The FIH study results are reported in the CSR (date 01 March 2011), based on the final FIH study CRF version date 25 January 2010 and the final study database.

2. STUDY OBJECTIVE(S) AND ENDPOINT(S)**2.1 Study Objective(s)**

The study objectives are,

- To determine the long-term safety profile of IMM-101 administered intradermally for extended use.
- To document the long-term clinical course of the patients previously enrolled in Study IMM-101-001.
- To monitor selected markers of tumour burden and immunological status.

The objective of this Statistical Analysis Plan (SAP) is to summarise the following outputs:

- Patient disposition
- Demographic characteristics
- Medical history
- Previous medications
- IMM-101 dose administration, time on study and exposure
- Injection site reactions
- Adverse events
- Overall Survival (OS)

The FIH and LTF combined data presentation objectives are to summarise the following outputs:

- Relevant medical events during the NPP (i.e. prior to entry to IMM-101-008)
- Anti-melanoma Cancer Therapies other than IMM-101 whilst on IMM-101 treatment
- IMM-101 administrations (from first dose of IMM-101 in the FIH study and including administrations during the LTF study)
- IMM-101 exposure
- Incidence and frequency of IMM-101-related treatment emergent AEs occurring following first dose of IMM-101 in the FIH study

2.2 Study Endpoint(s)

The Safety and Tolerability endpoints are:

- Local injection site tolerability
- Adverse Events with documentation of number, type and degree of toxicities as measured by the National Cancer Institute (NCI) Common Toxicity Criteria for Adverse Events (CTCAE) v4.0 [1] where appropriate.

The Efficacy endpoints are:

- Overall survival
- Reduction in metastatic disease.

Exploratory endpoints of change in markers of immune status are to be reported separately from the main endpoints of the study, and the analyses are not therefore described in this SAP.

3. STUDY DESIGN

The LTF study is an open label long-term follow-up study of patients with melanoma who were previously enrolled in the Phase I FIH study IMM-101-001. The study consists of two phases; screening and enrolment, then treatment.

The screening period lasted up to 28 days to establish eligibility. Once confirmed as eligible, patients receive treatment every 4 weeks or as close to this interval as is permitted due to practical or logistical considerations until death or withdrawal, unless such therapy is contraindicated, the patient does not wish to continue or the study is terminated by the Sponsor. The dose interval can be modified at the discretion of the Investigator provided the minimum period between doses is no less than 14 days.

IMM-101 can be stopped if deemed necessary by the Investigator and/or patient, for example, due to intolerable injection site reactions. In the event of an injection site reaction of Grade 3 and above, at the discretion of the Investigator, patients may be administered a half dose of the study drug (i.e., a single 0.05 mL intradermal injection of IMM-101) or the time interval between doses may be increased.

Patients can choose to withdraw from the study at any time and for any reason.

Protocol amendment 6.0 (dated 07 November 2014) allowed for a clinic telephone call to the patient to enquire about injection site reactions, adverse events, concomitant medications and any other concerns, if the patient does not attend for a study visit within a calendar month. Appropriate information is recorded in the CRF.

4. PLANNED ANALYSES

At the time of final analysis for the study, descriptive summaries of the results of the study will be provided along with data listings of the final study database. Summary statistics or frequency tables will be provided, where appropriate.

Section 9 provides details of the descriptive statistics and TFL shells are included in Section 13.

No formal statistical analyses of the results are anticipated and hence no statistical inferences will be made.

Planned analyses as detailed in the protocol are as follows:

The evaluation of safety and tolerability will be summarised using the Safety population and will be based on local and systemic toxicities (including injection site tolerability) which will be presented over the treatment period in standard frequency tables, overall and by number, degree and type. Adverse Events will

be presented descriptively to include related adverse events, serious adverse events (SAEs), and adverse events leading to withdrawal or death. The frequency and severity of injection site reactions, and all other safety parameters will be summarised.

All patients will have received IMM-101 in the context of both the Phase 1 study and, for the majority, on a Named Patient basis; therefore all AEs in this long term follow up study will be regarded as treatment emergent.

Efficacy will be presented using the Safety population and will be assessed through documenting the long-term clinical course of the patients previously enrolled in Study IMM-101-001 in terms of OS. Reduction in metastatic disease will be listed only.

Variables for the exploratory endpoints will be analysed and reported separately to the main efficacy and safety endpoints of the study.

The protocol specified that OS will be presented from enrolment into this study, in addition to time from initial diagnosis and enrolment into study IMM-101-001. Time zero for the OS analysis in this study (IMM-101-008) will be based on the date of Day 0 in this study and analysis of OS taking into account time from initial diagnosis and first dosing day in Study IMM-101-001 will not be included in this SAP as not all patients completing the FIH study entered the LTF study.

In addition to the above planned presentations, non-serious adverse events in LTF study patients will be tabulated and treatment-related treatment emergent AEs will also be presented combining data in these patients, from both the FIH and LTF studies.

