#### **3.3 CLINICAL FINDINGS**

**Study Number IMM-101-001:** This was an open-label, dose-escalation, intra-patient, placebo-controlled study, in adult patients with confirmed diagnosis of stage III or IV melanoma to evaluate the safety and tolerability of three doses of IMM-101.

A total of 19 patients were enrolled into the study between 10 March 2010 and 27 July 2010, and the study was completed by 23 September 2010; six patients received placebo followed by 3 doses of IMM-101 0.1 mg, six patients received placebo followed by 3 doses of

---

CONFIDENTIAL

Immudalon Therapeutics Ltd.  
[name]

IMM-101 0.5 mg, and six patients received placebo followed by 3 doses of IMM-101 1.0 mg, over a 4 week period. One patient received placebo followed by 2 doses of IMM-101 0.5 mg but was withdrawn after the second dose of IMM-101 as they were found retrospectively to have been ineligible at study entry due to brain metastases; an additional patient was recruited to this dose cohort to ensure data on six patients were collected.

The placebo injection was administered on Day -3 and the IMM-101 injections over a 4-week period (Day 0, 14 and 28). All injections were administered intradermally. At each dosing level, one patient was administered IMM-101 at least 24 hours in advance of the remaining patients in order to review safety evaluations and observe local injection site reactions. The decision to dose-escalate was preceded by a comprehensive review of safety data from the previous dose cohort.

There were no dose limiting toxicities observed and no evidence to suggest a clinically significant impact upon haematological indices, biochemical parameters or cardiac function. All documented changes in vital signs from screening to end of study were unremarkable.

There were no treatment-emergent adverse events (AEs) reported in the period following the placebo injection and before the first dose of IMM-101 – thus allowing a clear definition of the tolerability of the test product.

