### **3.7 POPULATION**

All surviving patients from the IMM-101-001 protocol (EudraCT number: 2009-012447-42) will be invited to enrol in the study by the Principal Investigator.

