### **4.2 RATIONALE**

No safety concerns were evident in the previous Phase 1 study which these patients all participated in, however, there was only relatively limited patient exposure to IMM-101 in the context of the study with each patient receiving just 3 doses on study.

All 18 eligible patients had completed the study by the end of September 2010 and the majority continued to receive IMM-101 on a named patient basis under the supervision of the Chief Investigator. As of August 2011, a number of patients have stopped treatment (3 died, 1 stopped due to pregnancy and 2 for unknown reasons). All remaining patients have expressed a wish to continue to receive treatment and the Chief Investigator has confirmed that they consider it in these patients' best interest to do so.

The Sponsor considers it more appropriate to continue treatment of this cohort of patients in the context of a formal long term follow up safety study rather than on a named patient basis so that the patients can be followed for long term safety.

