#### **Overall Survival (OS)**

OS is defined as the time from enrolment to death due to any cause. OS will be expressed from time of initial diagnosis, time of enrolment in the Phase 1 study as well as from time of enrolment in this long term follow up study.

Patients without a death date will be censored at the date the patient was last known to be alive.

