5. SAMPLE SIZE CONSIDERATIONS

Surviving patients from Study IMM-101-001 (EudraCT number: 2009-012447-42) who were continuing to receive IMM-101 on a Named Patient Programme (NPP) basis were invited to enrol into study IMM-101-008.

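### Overall survival is reported only from follow-up Day 0 in patients who entered IMM-101-008, so it is conditional on more than a year's prior survival and does not describe the IMM-101-001 cohort

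*SAP*

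**What the plan says.** Protocol section 4.1(b) and SAP section 2.1 share an objective, in the SAP's words "To document the long-term clinical course of the patients previously enrolled in Study IMM-101-001". SAP section 4 says efficacy will document that course in terms of OS.

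Protocol section 8.1 sets three time origins: "OS will be expressed from time of initial diagnosis, time of enrolment in the Phase 1 study", and entry to the follow-up study. SAP section 4 acknowledges all three, fixes time zero at Day 0 of IMM-101-008, and says that analysis from the other two "will not be included in this SAP as not all patients completing the FIH study entered the LTF study". SAP sections 8.3 and 10 define OS from Day 0, and Table 8 and Figure 2 are the only OS outputs.

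The population is fixed separately. Protocol sections 10.1.1.3 and 10.7.1 put efficacy on the Safety set, and SAP section 6 defines this as patients dosed at least once in the follow-up study.

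On what came before, protocol section 3.3 reports "A total of 19 patients were enrolled into the study between 10 March 2010 and 27 July 2010" and that "the study was completed by 23 September 2010". Protocol section 4.2, writing of the 18 eligible patients, adds: "As of August 2011, a number of patients have stopped treatment (3 died, 1 stopped due to pregnancy and 2 for unknown reasons".

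The documents differ on who was invited. Protocol section 3.7 invites "All surviving patients from the IMM-101-001 protocol". SAP section 5 says that survivors "who were continuing to receive IMM-101 on a Named Patient Programme (NPP) basis were invited".

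**The concern.** The objective names one group of patients and the OS output describes another. A patient reaches Table 8 only by living until the follow-up study opened, entering it and being dosed. The curve then starts at 100% on that day, although some of the cohort had already died.

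The output is a valid description of entrants after entry. It does not give the survival of the patients treated in IMM-101-001. Nothing in the titles of Table 8 or Figure 2 says that the result is conditional on entry, and no planned table accounts for the Phase I patients who never entered.

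**Working it through.** The plan states no sample size, event target or significance level (protocol sections 10.2 and 10.3), so there is no design figure to reproduce. The check uses dates and counts.

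**Survival built in before Day 0.** Inputs: Phase I enrolment from 10 March to 27 July 2010 (protocol section 3.3), and protocol version 1.0 dated 15 September 2011 (protocol Appendix 4), before which nobody could have had a Day 0.

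- First enrolled: 10 March 2010 to 15 September 2011 = 554 days; 554/365.25 = 1.52 years.
- Last enrolled: 27 July 2010 to 15 September 2011 = 415 days; 415/365.25 = 1.14 years.
- Latest possible first dose, inferred as Phase I completion minus the 28-day dosing period: 23 September minus 28 days = 26 August 2010, giving 385 days (1.05 years).

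These are minima, because actual Day 0 dates are later.

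**Deaths that cannot appear.** Three deaths were reported by August 2011, before version 1.0. Those patients could not be dosed in the follow-up study. 3/18 = 16.7% of eligible patients. Three is also a minimum: the later status of the two who stopped for unknown reasons, and of the ineligible nineteenth patient, is not given.

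**Cohort survival at the start of the follow-up study.** At most (18 − 3)/18 = 15/18 = 83.3%. Counting the nineteenth patient as alive gives 16/19 = 84.2%. The Day 0 curve shows 100% by construction.

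**What a Day 0 reading implies for the cohort.** Let S be the Day 0 survival estimate, E the number of entrants and n = 18. The remaining n − E − 3 patients were not reported dead and did not enter.

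- Lower bound, all of them dead by that time: S × E/n.
- Upper bound, all of them alive: (S × E + n − E − 3)/n.

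E is not stated, so two values are assumed. E = 12 is what remains if the six who had stopped treatment (3 + 1 + 2) did not enter. E = 10 is suggested only by the 2×5 panel layout of Figures 1a and 1b.

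| Day 0 reading S | E = 12 of 18 | E = 10 of 18 |
|---|---|---|
| 100% | 67% to 83% | 56% to 83% |
| 75% | 50% to 67% | 42% to 69% |
| 60% | 40% to 57% | 33% to 61% |
| 50% | 33% to 50% | 28% to 56% |

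For S = 60% and E = 12: 0.60 × 12 = 7.2; 7.2/18 = 40%; (7.2 + 3)/18 = 57%. For E = 10: 6.0/18 = 33%; (6.0 + 5)/18 = 61%.

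**What restoring the protocol's origins would do.** Starting the clock at Phase I entry or diagnosis, in the Safety set only, recovers none of the three deaths. Each entrant's time from Phase I enrolment would include at least 415 to 554 days in which death was impossible by selection. The SAP's reason is therefore a sound objection to that analysis. It is not a reason to leave the cohort undescribed, and the SAP already works with the relevant dates: first Phase I dose for Table 9b, and date of diagnosis for Table 3a.

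**The case against.** The strongest defence is that the change is open and allowed. SAP section 4 states the protocol's three origins, the change and the reason, and protocol section 10.6 lets a final SAP document deviations. This stands. A reader might infer a concealed change; the documents do not support that. The residual gap is that SAP section 11 lists only the move from enrolment to Day 0, not the two dropped origins.

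Second, a reader might infer that dropping the origins is what removed the deaths. It is not. The protocol's own Safety set removes them, so the protocol's analysis would not have described the whole cohort either.

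Third, the outputs are not mislabelled as to origin. Table 8's footnote gives the Day 0 formula, Figure 2's axis is time after Day 0, the SAP disclaims inference, and protocol section 3.4 says the study is not designed to show efficacy. That answers the origin, but not the selection or the prior deaths, which neither output mentions.

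Fourth, it would be too strong to say that the objective goes unanswered. For entrants, Tables 3a, 3b, 6 and 9b, Figure 1b and Listings 4b, 11 and 17 document much of the course. What is missing is cohort survival.

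Fifth, full-cohort data may not be available. Information from the named patient programme enters only where the follow-up CRF recorded it, access to intervening history rests on consent under inclusion criterion 2, and the post-study survival CRF covers only withdrawn follow-up patients. Counting known deaths while censoring living non-entrants at the end of Phase I would bias the curve downward. This stands and limits what can be asked.

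**Conclusion.** The concern holds in this form: the only OS output is conditional on at least 415 to 554 days' survival from Phase I enrolment and on entry to IMM-101-008. It cannot include three of 18 eligible patients known to have died, and it starts at 100% where the cohort stood at 83% at most. The SAP rejected an unsound alternative and left nothing in its place.

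Two stronger readings are tempting. One is a single correction factor: multiply any Day 0 figure by 15/18, so that 60% becomes 50%. That needs all survivors to have entered, or non-entrants to have fared like entrants, and neither is documented. The supportable statement is a range, 40% to 57% or 33% to 61% under the assumed entrant numbers. The second range reaches just above 60%, so at later times even the direction of the difference is not established.

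The other is that every entrant had stayed on drug. Only SAP section 5 says this. Protocol section 3.7 invites all survivors, protocol section 7.3 refers to most patients, SAP section 4 to the majority, and Table 4 has a row for patients with no intervening doses.

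The conclusion assumes that the three deaths fall among the 18 eligible patients, as protocol section 4.2 reads. The SAP cites protocol version 9.0, while the supplied amendment log ends at amendment 7.0; SAP section 4 itself confirms the three origins.

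**What to change.** 1. Title Table 8 and Figure 2 *OS from LTF Day 0, conditional on survival to and entry into IMM-101-008*, with a footnote stating the three deaths reported before the study.
2. Add to Table 1 or Table 8 an accounting of all 19 Phase I patients: died before the follow-up study, alive and not enrolled, enrolled, status unknown.
3. For the protocol's other origins, present OS from first Phase I dose and from diagnosis in entrants, using Kaplan-Meier with delayed entry at Day 0. Label it as conditional and note the small early risk sets. It removes the guaranteed survival time but does not recover the three deaths, so the footnote is still needed. If entry depended on continued treatment, independence of entry is also doubtful.
4. Present full-cohort OS from first Phase I dose only if death and last-known-alive dates can be obtained on the same basis for all non-entrants, with the permissions needed. Otherwise give best-case and worst-case bounds as above.
5. List the two dropped OS origins in SAP section 11.
6. Reconcile protocol section 3.7 with SAP section 5 on who was invited.

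Items 1, 5 and 6 are wording. Item 2 is a short table, with unknown status shown as such. Item 3 uses dates already held for entrants. Only item 4 needs new data. The price is a small amount of extra output and a less favourable description of survival.
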